### **Sample size**

Although all clinical trials require sample size justification, formal sample size calculations are not necessarily appropriate for feasibility trials (Billingham, Whitehead, & Stevens, 2013). In this study, qualitative acceptability data will be used for further development of the intervention as necessary. Quantitative data (such as feedback ratings and changes in depression) will inform future research about the acceptability of the intervention in its current form and provide an estimate of the effect size for depression. A minimum sample size of 12 can be justified based upon precision of the estimates to be used in future research (Julious, 2005), although extra participants need to be recruited to allow for attrition. A meta-analysis of internet-based CBT found that attrition was 48% at the 75th percentile of studies (Andrews et al., 2018). To allow for up to 48% attrition, it will be necessary to recruit 23 participants to provide the minimum sample size of 12.

The maximum sample size is dictated by the available resources to facilitate the intervention. Based on clinical experience of providing email and telephone guidance to patients undertaking cCBT, it is expected that providing email support will take around 10 minutes per week per patient on average. Given the researcher's working pattern, up to nine hours per week could be allocated for directly facilitating the intervention (approximately half of the researcher's part-time hours). This leads to a maximum of 54 ( $[9 \times 60]/10$ ) participants that can be provided with email support at any one time. Although it would be possible to include more participants in the study due to the rolling nature of recruitment, there are diminishing returns on the value of increasing the sample size, as gains in the precision of estimates become less pronounced (Hertzog, 2008; Julious, 2005). It therefore seems logical to set 54 participants as the maximum sample size for the study.

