## **Acceptability and feasibility criteria**

Acceptability of intervention overall: The percentage of eligible participants who access the webpages will be calculated using Qualtrics data and user logins to the website. The intervention will be considered acceptable if at least 66% of eligible participants log into the website during their sixth week of the study. This criterion was chosen as a recent meta-analysis of computerised CBT for depression and anxiety disorders reported a median retention rate of 66% (Andrews et al., 2018).

Feasibility of providing online self-help: All eligible participants should be able to access the website, so if less than 90% of eligible participants log into the website during their first week of the study, this may suggest that there were problems with accessing the self-help website. This criterion was chosen as more than one in ten people having

difficulty accessing the website is analogous to experiencing a ‘very common’ side effect of a medication (NHS, 2018). User logins for subsequent weeks of the intervention will also be recorded.

Feasibility of providing guidance: Researcher time spent providing email guidance will be recorded, and will be considered feasible if this takes 120 minutes or less per patient over the study period. This criterion is derived from guidance on individual guided self-help interventions for people with depression, which typically consist of up to 240 minutes overall (up to eight sessions at 30 minutes each; NICE, 2010; National IAPT Programme, n.d.): if providing email guidance takes over half the amount of time needed for individual guided self-help programmes, then it cannot reasonably be argued to be “limited facilitation” (NICE, 2010, p. 23). The percentage of participants who requested additional support via email will also be recorded. These figures will inform future trials and implementation of guided self-help for people with skin conditions within health services.

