### **Estimated timescale**

A previous study of an online intervention for people with heterogeneous skin conditions recruited 176 eligible participants over approximately three months (Hudson, 2015), using similar recruitment techniques. This equates to recruitment of 59 participants per month. The current study has one additional exclusion criterion (mild–moderate level of depressive symptoms) compared to Hudson's (2015) study, so recruitment rates may be somewhat lower. Accordingly, it is expected that recruitment will be completed within 6 weeks. In the current study it is hoped to recruit participants primarily from skin condition charities/organisations so that university students are not over-represented in the sample. However, if less than half of the minimum sample required ( $n = 12$ ) have been recruited three weeks after the study has been advertised by skin condition organisations, the study will be subsequently advertised using the researcher's and the University of Sheffield's volunteer lists. Recruitment will be closed after six weeks if the minimum sample size has been achieved or earlier if the maximum sample size has been achieved. Once recruited, participants will remain in the study for seven weeks (six weeks of the intervention plus follow-up one week later). It is therefore expected that the study overall will be completed in 13 weeks.

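### The recruitment minimum of 23 is rounded down from 23.08; rounding up gives 24, a minor correction that should carry through to the closing rule

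*Combined protocol and SAP*

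**What the plan says.** The Sample size section gives the reason for the minimum: "A minimum sample size of 12 can be justified based upon precision of the estimates to be used in future research". It adds that more must be recruited to cover attrition and takes the allowance from a meta-analysis of internet-based CBT, where "attrition was 48% at the 75th percentile of studies". It then concludes that, for attrition up to that rate, "it will be necessary to recruit 23 participants to provide the minimum sample size of 12". The upper limit comes from the time available for email support: "It therefore seems logical to set 54 participants as the maximum sample size for the study".

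Estimated timescale uses the minimum in its stopping rule for enrolment: "Recruitment will be closed after six weeks if the minimum sample size has been achieved or earlier if the maximum sample size has been achieved". The same section keeps each participant in the study for seven weeks.

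For its login criterion, the section Acceptability and feasibility criteria cites the same meta-analysis, which "reported a median retention rate of 66" per cent.

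**The concern.** A minimum that must hold at attrition of up to 48% has to be rounded up, because rounding down leaves the expected number below the minimum at the very rate allowed for. The plan's figure sits just on the wrong side.

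The figure also governs conduct, since enrolment may close at six weeks once the minimum is reached. Follow-up is at seven weeks, so at that point nobody has reached the final assessment and attrition to the endpoint is not yet known. The plan has no rule for reopening. If enrolment ended close to the minimum, any shortfall below 12 would come to light only after recruitment had stopped.

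What is at stake is the precision basis of the minimum for the paired pre–post estimates. The login criteria use all eligible participants as denominator, so they do not depend on how many complete the final measures.

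**Working it through.** **Inputs**

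- Minimum to remain: 12 (Sample size).
- Attrition allowed for: d = 0.48 (Sample size).
- Stated number to recruit: 23 (Sample size).
- Median retention: 66%, so attrition of 34% (Acceptability and feasibility criteria).
- Maximum: 54 (Sample size).

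**Reproducing the plan's figure**

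n/(1 − d) = 12/(1 − 0.48) = 12/0.52 = 23.08. To the nearest integer this is 23, the plan's figure. The correct inflation formula was used; the mistaken form n(1 + d) would have given 12 × 1.48 = 17.8, so 18. Rounded up, as a minimum requires, the answer is 24.

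**Expected number remaining at 48% attrition**

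- 23 recruited: 23 × 0.52 = 11.96, which is 0.04 below 12.
- 24 recruited: 24 × 0.52 = 12.48.

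**In whole people**

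From 23, exactly 12 remain if 11 are lost, and 11/23 = 47.8%. So 23 covers attrition up to 47.8%, just under the stated 48%. From 24, 12 remain if 12 are lost, which is 50%.

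**Chance of at least 12 remaining**

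The plan gives no such probability. These are exact binomial probabilities, P(X ≥ 12) with X ~ Binomial(n, 1 − d), assuming independent dropout with a common probability.

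| Attrition | 23 recruited | 24 recruited |
|---|---|---|
| 34% | 94.4% | 96.7% |
| 40% | 83.6% | 88.6% |
| 43% | 75.2% | 81.6% |
| 48% | 57.7% | 65.6% |

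The 43% row is the intervention-arm attrition that the protocol's background reports for an earlier computerised programme in psoriasis. At 48% attrition, 27 recruited give 83.6%, 29 give 90.8% and 31 give 95.2%. With 54 recruited, the probability exceeds 99.9%.

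**What one participant fewer costs in precision**

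The 95% half-width for a mean change, in units of the SD of change, is t(0.975, k − 1)/√k. It is 0.635 for k = 12 and 0.672 for k = 11.

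**The case against.** The strongest case on the other side is that there is almost nothing here. The formula is correct, the gap is 0.04 of an expected participant, and losing 11 of 23 is 48% when rounded. All of that stands, and it is why the point is minor.

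A reader might go further and infer from the 58% that the plan fails at the attrition it claims to cover. The documents do not support that:

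- Inflating by n/(1 − d) targets the expected number, so a probability not far above one half is normal at the planning value. The corrected 24 gives only 66%.
- The plan promises no level of assurance and says that formal calculations are not necessarily appropriate for feasibility trials. A target of 29 for about 90% assurance would be an added standard. Its absence is not an error.
- The 48% is a deliberately pessimistic value, the 75th percentile of studies. At the 34% attrition implied by the median, 23 already gives 94%.
- The 58% applies only if enrolment ends at exactly 23. Enrolment does not stop on reaching the minimum; it runs for six weeks unless 54 is reached first. Estimated timescale cites 59 participants per month in a similar study. Six weeks is 6 × 12/52 = 1.38 months, so that rate would give about 82. The plan expects somewhat lower rates, but 23 would be only about 28% of that number (23/82).

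These arguments limit the consequence but do not make 23 the right rounding. The plan words 23 as what is needed at up to 48%, and at 48% it falls just short. The order of closing (six weeks) and follow-up (seven weeks) is also a fact, though it matters only if recruitment is slow and attrition is high.

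**Conclusion.** The stated recruitment minimum is one too low. It should be 24, because 12/0.52 = 23.08 must be rounded up and 23 gives 11.96 expected at 48% attrition. This part is arithmetic and needs no assumption beyond the plan's own inputs.

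The point is minor. The inflation method is sound, the shortfall is 0.04 of an expected participant, and enrolment may run to 54. The figure is worth correcting because it is a stated sample size and the closing rule depends on a minimum. It is also worth saying what the figure delivers, since neither 23 nor 24 secures 12 with high probability if attrition really is 48%. The probabilities given rest on independent dropout with a common rate. Any dependence between participants would change them, but not the rounding.

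**What to change.** In Sample size, replace 23 by 24 and add a sentence such as: *At 48% attrition, 24 recruits yield 12 on average (12.48 expected); assuming independent dropout, the chance of at least 12 is about 66% at 48% attrition and about 97% at 34%.*

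In Estimated timescale, state that the minimum in the closing rule is 24 recruited. At present the rule does not say whether it means 12 or the inflated number. The same wording can settle the three-week trigger for wider advertising, where the n = 12 in brackets could be the minimum itself or about half of the inflated figure (half of 24 is exactly 12).

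The sponsor may add, as optional information, that 29 would give about 90% assurance at 48% attrition. This is not a required change. The cost is a few words in two sections, with no change to the maximum, the analysis or the resources.

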### **Estimated timescale**

A previous study of an online intervention for people with heterogeneous skin conditions recruited 176 eligible participants over approximately three months (Hudson, 2015), using similar recruitment techniques. This equates to recruitment of 59 participants per month. The current study has one additional exclusion criterion (mild–moderate level of depressive symptoms) compared to Hudson's (2015) study, so recruitment rates may be somewhat lower. Accordingly, it is expected that recruitment will be completed within 6 weeks. In the current study it is hoped to recruit participants primarily from skin condition charities/organisations so that university students are not over-represented in the sample. However, if less than half of the minimum sample required ( $n = 12$ ) have been recruited three weeks after the study has been advertised by skin condition organisations, the study will be subsequently advertised using the researcher's and the University of Sheffield's volunteer lists. Recruitment will be closed after six weeks if the minimum sample size has been achieved or earlier if the maximum sample size has been achieved. Once recruited, participants will remain in the study for seven weeks (six weeks of the intervention plus follow-up one week later). It is therefore expected that the study overall will be completed in 13 weeks.

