Skin conditions are among the most common health complaints in the world: skin disease is the fourth leading cause of nonfatal disease burden (Hay et al., 2013). In the UK, an estimated 54% of the population experience a skin condition each year. While the majority (69%) of these people self-care, almost 13 million people in England and Wales visit their GP each year for skin complaints, with 0.8 million people being referred on for specialist care (All Party Parliamentary Group on Skin, 2013). While some skin conditions are resolved relatively quickly, others are life-long conditions. The impact of skin conditions can be considerable, for example, psoriasis has been found to have a similar impact on health-related quality of life as diseases such as cancer, arthritis, and heart disease (Rapp, Feldman, Exum, Fleischer, & Reboussin, 1999). As well as causing symptoms that are difficult to live with, skin conditions can impact other areas of individuals' lives, including work/school, daily activities, leisure, personal relationships and socialising (de Aruda & de Moraes, 2001; Dures, Morris, Gleeson, & Rumsey, 2011; Sampogna, Tabolli, & Abeni, 2012). A further, related, impact of skin conditions is on mental health. Living with a chronic skin condition can involve ongoing difficulties in the aforementioned areas, which can be sources of stress. In addition, people with skin conditions may experience appearance concerns and self-criticism if they perceive themselves to be falling short of their ideal standards due to their skin condition. This may lead to feelings of shame and anxiety. Indeed, skin conditions have been found to be associated with higher than average levels of psychological distress. Studies have found overall psychiatric morbidity among dermatology patients of 25.2% (Picardi, Abeni, Melchi, Puddu, & Pasquini, 2000), and significantly higher rates of depression, anxiety and suicidal ideation than people without skin conditions (Dalgard et al., 2015).

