### **Psychological treatments for people with skin conditions**

There are few psychological treatments available specifically for people with skin conditions: the ones most used are habit reversal, cognitive behavioural therapy (CBT), arousal reduction and combined techniques (Lavda, Webb, & [name], 2012). Habit

reversal focuses on reducing itch/scratch cycles, to improve the condition of the skin in pruritic conditions. CBT focuses on changing unhelpful thoughts and behaviours associated with the skin condition while arousal reduction focuses on reducing physiological arousal through techniques such as relaxation or meditation.

Psychological treatments for people with skin conditions often focus on anxiety rather than depression (for example, A. Clarke, [name], Jenkinson, Rumsey, & Newell, 2014), as it has been noted that people with conditions that alter their appearance can experience similar difficulties to people with social anxiety disorder, such as fear/avoidance cycles about public scrutiny (Bessell & Moss, 2007). However, not all people with skin conditions experience difficulties with (social) anxiety as their primary psychological problem. Clinical depression has been found to be present in 10.1% of dermatology patients (Dalgard et al., 2015). Although anxiety problems were more common in this population (17.2%), the odds ratio for depression was higher (Dalgard et al., 2015). Furthermore, depression is associated with a higher average level of disability than anxiety disorders (World Health Organisation, 2017), and so there is a need to develop psychological interventions for people with skin conditions that focus on depression.

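### Does the six-week closing rule let recruitment stop at 12 enrolled rather than 23?

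*Combined protocol and SAP*

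**What the plan says.** The Sample size section justifies a minimum of 12 on precision, "although extra participants need to be recruited to allow for attrition". Allowing for 48% attrition, it concludes that "it will be necessary to recruit 23 participants to provide the minimum sample size of 12". The maximum is 54, set by how many people the researcher can support by email at one time.

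The Estimated timescale section then gives two operating rules. At week three, advertising widens to volunteer lists "if less than half of the minimum sample required", followed by n = 12 in brackets, have been recruited. At week six, "Recruitment will be closed after six weeks if the minimum sample size has been achieved", or earlier if the maximum is reached. The section adds: "Once recruited, participants will remain in the study for seven weeks". Its accrual benchmark is an earlier online study that "recruited 176 eligible participants over approximately three months". It expects a somewhat lower rate here, because this study also restricts entry by depression score.

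**The concern.** The Sample size section uses the term minimum sample size twice, each time for 12, and never calls 23 a minimum. The closing rule uses the same term without a number. Nobody can have finished a seven-week participation by week six, so the rule must count people enrolled. Carrying the term over literally gives closure at 12 enrolled, which cancels the attrition allowance made one section earlier.

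The bracketed 12 in the week-three trigger does not settle the matter, because 12 is both the post-attrition minimum and, after rounding, half of 23. The trigger could therefore fire below 6 or below 12.

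At stake is the number of people behind the effect-size estimates named in the Aims, and behind the percentages in the Acceptability and feasibility criteria, whose denominator is eligible participants. There is also a point of principle: a closing rule should not be open to interpretation once accrual is known.

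**Working it through.** **The plan's own figure.** Inputs from the Sample size section are 12 wanted and 48% attrition. 12 / (1 − 0.48) = 23.08. Strict rounding up gives 24, but 23 × 0.52 = 11.96, and losing 11 of 23 is 47.8% and leaves exactly 12. The stated 23 stands.

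**Where the readings part.**
- Week three: half of 12 is 6; half of 23 is 11.5, so 12 in whole people. The readings differ with 6 to 11 enrolled.
- Week six: the readings differ with 12 to 22 enrolled.

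**Cost of closing inside the week-six window.** Expected completers are n × 0.52. The 95% CI half-width for mean change, in SDs of change, is t(0.975, m − 1)/√m, with m the completers rounded to a whole number.

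| Enrolled | Expected completers | Half-width |
|---|---|---|
| 12 | 6.24 | 2.571/√6 = 1.05 |
| 17 | 8.84 | 2.306/√9 = 0.77 |
| 22 | 11.44 | 2.228/√11 = 0.67 |
| 23 | 11.96 | 2.201/√12 = 0.64 |

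The 48% is the 75th percentile of the attrition reported in the cited meta-analysis. At the 66% median retention quoted in the Acceptability and feasibility criteria, 12 enrolled gives 12 × 0.66 = 7.92 completers (half-width 2.365/√8 = 0.84), and 23 gives 15.18.

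**How slow accrual must be.** 176/3 = 58.7 per month. Six weeks is 6/(52/12) = 1.385 months, so the cited rate gives 58.7 × 1.385 = 81.2. The window of 12 to 22 corresponds to 12/81.2 = 14.8% up to 22/81.2 = 27.1% of that rate, so accrual must fall by about 73% or more. By contrast, 54/81.2 = 66.5%: two-thirds of the cited rate already reaches the maximum.

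**What the wording points to.**
- The rule governs recruitment, and the only figure the plan gives as the number to recruit, as a floor, is 23.
- The rule pairs the minimum with the maximum of 54, which is a count of people enrolled.
- Nobody can have completed by week six, so a post-attrition count cannot be what the rule checks.
- Half of 23 is 11.5, which explains a bracketed 12 placed after a phrase about half the sample.
- With a trigger of fewer than 12, a study on steady course for 12 to 22 at week six (6 to 11 at week three) would already have widened its advertising.

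**The case for a change.** The strongest reply is that the plan's own vocabulary favours 12, and that a literal reader could close at 12 enrolled without breaching the text. The damage would be real: the probability of at least 12 completers at 48% attrition is 0.0004 with 12 enrolled and 0.58 with 23. Nor would it stop at the completer analysis. Just meeting the 66% acceptability criterion means 8 of 12 (exact 95% CI 35% to 90%) or 16 of 23 (47% to 87%). The protocol itself foresees slow accrual, since it writes a back-up trigger, and it gives no figure for the share of volunteers who would score 10 to 20 on the depression scale.

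Much of this stands. The term is used loosely, the feasibility percentages depend on the number enrolled, and the eligible share is unknown. That share cannot be recovered from the background figures. Applying the 25.2% psychiatric morbidity to 81.2 gives about 20 at week six, inside the window; applying the 10.1% clinical depression gives about 8, outside it. Neither measures mild to moderate scores among people answering this advertisement, so together they establish nothing.

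What does not stand is that the two readings are equally live. The literal one requires the researcher to ignore an explicit statement, one section earlier, of how many must be recruited and why. The figure of 6 completers also belongs only to the bottom edge of the window; at the top edge, 11.44 against 11.96 is no practical difference.

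**Conclusion.** This is loose wording, not an arithmetic error, and no change follows. The closing rule is sensibly read as 23 enrolled and the week-three trigger as fewer than 12; the needed number is already printed in the Sample size section. The readings lead to different action only with 6 to 11 enrolled at week three or 12 to 22 at week six, the latter needing accrual at about 27% or less of the cited rate. If recruitment did close in that window, expected completers at 48% attrition would run from about 6 to about 11, against about 12 as planned.

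The conclusion rests on two assumptions: that the researcher applies the attrition allowance the plan itself states, and that accrual is, as the plan expects, only somewhat below the earlier study's rate. The second cannot be verified from the document. If it fails, the first still leads to the intended number.
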